3.3 Study Treatments and Assessments

Following screening, enrollment, and randomization, subjects will be issued a 4-week supply of investigational product based on the individual subject's projected usage. After a screening period of up to 35 days, women will be randomized to receive either EVO100 or placebo:

EVO100 vaginal gel is supplied in individually wrapped 5 g single-dose, pre-filled vaginal applicators. EVO100 is a viscous, off white to tan gel of uniform consistency. Its active ingredients are lactic acid United States Pharmacopeia (USP), citric acid USP, and potassium bitartrate USP.

Subjects will be asked how many pre-filled applicators they need, based on their anticipated number of sexual encounters per 4 weeks. Up to 3 boxes may be dispensed to meet their anticipated need. Additional boxes may be dispensed between visits, if needed.

At visits 2 through 4, during the intervention period, subjects will return all unused product and will be issued a new 4-week supply of investigational product based on projected usage.

Unopened kits may be re-dispensed to the same subject, provided the subject follows specified storage instructions. The staff may also re-dispense to the same subject individually wrapped product from an open kit provided specified storage instructions have been followed and the staff completes product accountability reconciliation activity. Subjects may be issued additional investigational product, as needed, should their supply be exhausted prior to the next study visit; however, excessive product usage should be brought to the attention of the Investigator and Sponsor. At Visit 5, subjects will return all unused product.

Table 1 shows the study dosing for each intervention group.

Table 1: Investigational Product Dosing

Intervention Group	EVO100 vaginal gel	Placebo
Group A	865 subjects, 5 g dose applied up to 1 hour prior to coitus	N/A
Group B	N/A	865 subjects, 5 g dose applied up to 1 hour prior to coitus

Table 2: Schedule of Study Assessments

Study Visit (V)	Screening Visit 0 ⁽²⁾	Intervention Period ⁽¹⁾					Post-Intervention Follow-up/Visit 6
		Enrollment/Visit 1 ⁽³⁾	Visit 2 ⁽³⁾	Visit 3 ⁽³⁾	Visit 4 ⁽³⁾	Visit 5 ⁽³⁾⁽⁵⁾	
Study Week	-5.0 to 0 weeks (-35 to 0 days)	0	4 ⁽⁴⁾	8 ⁽⁴⁾	12 ⁽⁴⁾	16 ⁽⁴⁾	20
Investigational Product Dispensed		X	X	X	X		
Informed Consent/HIPAA	X						
Demographic Information	X						
Inclusion/Exclusion	X	X					
Confirm Eligibility Criteria		X					
Concomitant Medications	X	X	X	X	X	X	X
AE Assessment	X	X	X	X	X	X	X
Medical/Sexual History	X	X	X	X	X	X	X
Last Menstrual Period	X	X	X	X	X	X	X
Physical Exam		X					
Targeted Physical Exam ⁽⁶⁾			X	X	X	X	X
Body Weight/Height		X					
Vital Signs		X					
Gynecologic Exam		X				X ⁷	X ⁷
Urine HCG	X	X	X	X	X	X	X
Vaginal pH		X					
Self-collected CT/GC NAAT			X	X	X	X	X
Clinician-collected CT/GC NAAT	X	X					
eDiary Setup		X					
eDiary Review			X	X	X	X	X
Female Sexual Function Index (FSFI)	X	X	X	X	X	X	X
PROMIS Sexual FS (PROMIS® Brief Profile Sexual Function and Satisfaction)	X	X				X	X
Subject Sexual Impact Questionnaire			X	X	X	X	X
Product Satisfaction Questionnaire			X	X	X	X	X

Patient Global Impression of Change (PGIC)		X				X	X
Return Unused Study Product			X	X	X	X	

Abbreviations: AE = adverse event, CT = *Chlamydia trachomatis*, eDiary = electronic diary, GC = *Neisseria gonorrhoeae*, HCG = human chorionic gonadotropin, HIPAA = Health Insurance Portability and Accountability Act, NAAT = nucleic acid amplification test; V = study visit.

⁽¹⁾ The intervention period is defined as Visits 1 to 5. In the event a subject has CT or GC infection diagnosed at a local healthcare facility during the period between visits, the infection and treatment will be documented and every effort to obtain a medical record will be made.

⁽²⁾ Screening period may be up to 35 days. If subjects NAAT results are positive, they will be first treated by SOC then will return 3-4 weeks after Screening Visit (at least 21 days after treatment) for Enrollment/Visit 1. If the screening period extends past 35 days, subjects will not be enrolled and will need to be rescreened.

⁽³⁾ Subjects must be asked to abstain from vaginal intercourse in the 24 hours preceding Study Visits 2 through 5.

⁽⁴⁾ Subjects will be asked to return \pm 7 days within each visit window.

⁽⁵⁾ The procedures for Visit 5 should be followed for the Early Termination Visit.

⁽⁶⁾ For unscheduled visits: includes provision to contact subjects or allow unscheduled visits for managing AEs.

⁽⁷⁾ The gynecologic examination will be conducted during unscheduled visits, as necessary and during end of study and end of treatment visits. The gynecologic examination will not be conducted if the end of study/end of treatment visit is remote due to COVID-19.

4 STUDY ENDPOINTS

4.1 Primary Endpoint

- The primary efficacy endpoint is the proportion of subjects who are defined as study successes versus study failures among the intervention groups (EVO100 or placebo).
Estimand Framework
 - FDA Submission
 - Success is defined as subjects completing the trial to Visit 5 without any of the following: CT/GC infection, usage of prohibited antibiotics during the study, an invalid CT/GC test at Visit 5.
 - The mITT population will be used, and the Chi-Square test will be used to compare the failure rates in EVO100 and placebo.
 - EMA Submission
 - The parallel primary efficacy endpoints define success through Visit 5 as:
 - CT Infection Endpoint:
 - The proportion of subjects without a CT infection, CT prohibited antibiotics, or invalid Visit 5 CT test.
 - GC Infection Endpoint
 - The proportion of subjects without a GC infection, GC prohibited antibiotics, or invalid Visit 5 GC test.
 - The mITT population will be used and the Chi-Square test will be used to compare the failure rates in EVO100 and placebo.

Note: These two parallel primary endpoints enable efficacy to be assessed separately for CT and GC. In this way, if the study is successful for either CT or GC but not for both, an indication for prevention of just one of the two pathogens could still be granted. Both primary endpoints will be tested at the 0.05 significance level (with no adjustments for multiplicity of statistical testing).

4.2 Secondary Endpoint

The secondary outcome for this study will be assessing the incidence of AEs (descriptive analysis).

Secondary outcomes for the FDA submission will include the separate CT and GC infection endpoints used in the EMA primary endpoint.

4.3 Exploratory Endpoints

Exploratory assessments include:

- Comparison of the proportion of subjects with overall sexual satisfaction using the female sexual function index (FSFI) overall sexual satisfaction question at Visit 5 and not having a CT or GC infection.
- Comparison of the proportion of subjects with overall sexual satisfaction using the FSFI overall sexual satisfaction question at Visit 5.
- Comparison of the proportion of subjects reporting overall product satisfaction at Visit 5.

- Comparison of compliance with EVO100 vaginal gel usage versus placebo usage during study (rate of product use adherence versus placebo).
- Subgroup analyses of the primary endpoint (the proportion of subjects who are defined success versus failure) will be performed for the following:
 - Subjects with 0%, >0% and <20%, ≥20% and <40%, ≥40% and <60%, ≥60% and <80%, ≥80% and <100%, ≥80% and ≤100%, and 100% product use adherence.
- Descriptive analysis of failure components for the FDA and EMA primary endpoints.
- Comparison of PROMIS Sexual Function and Satisfaction (PROMIS SexFS), Pain and Lubrication subscales with EVO100 vaginal gel usage versus placebo.
- Comparison of FSFI Lubrication and Pain subscales with EVO100 vaginal gel usage versus placebo.
- Comparison of Patient Global Impression of Change (PGIC) with EVO100 vaginal gel usage versus placebo.

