8.6.3 Analysis of Exploratory Endpoints

The following summary and analysis will be provided for the exploratory endpoint using mITT population:

Patient-reported outcomes measures for this study are to evaluate the efficacy of EVO100 vaginal gel in the prevention of urogenital CT and GC infection by assessing the following proportions of subjects:

- With overall sexual satisfaction using the FFSI overall sexual satisfaction question at Visit 5 (i.e., at least through study day 105) and not having a CT or GC infection using FDA primary endpoint rules.
- With overall sexual satisfaction using the FFSI overall sexual satisfaction question at Visit 5 (i.e., at least through study day 105).
- Reporting overall product satisfaction at Visit 5 (i.e., at least through study day 105).
- A subset analysis of the primary endpoint (FDA rules) looking at results based on prior infection documentation will be performed.

Above endpoints will be compared against placebo based on Chi-Square test. The estimated difference in proportions, 95% confidence interval, and p-value will be presented. A two-sided 5% type I error rate ($\alpha=0.05$) will be used. The Fisher's Exact test will be conducted in place of the Chi-Square test if necessary due to issues with the expected cell counts.

From the FFSI questionnaire, question (#16) "over the past 4 weeks, how satisfied have you been with your overall sexual life?" will be considered for sexual satisfaction. The question from product satisfaction questionnaire "How satisfied are you with the study product?" will be used

to assess the overall product satisfaction. Responses will be categorized as satisfied (i.e., combined responses of very satisfied, moderately satisfied, about equally satisfied and dissatisfied) and dissatisfied (i.e., combined response of moderately & very dissatisfied) for the comparison.

Additional exploratory endpoints are:

- Compliance with EVO100 vaginal gel usage versus placebo usage during study (rate of product use adherence and placebo) will be summarised descriptively (see [section 8.5](#) for more details).
- The proportion of subjects who are defined success versus failure (FDA primary endpoint) will be summarized using the below adherence categories by treatment groups. The estimated difference in proportions, 95% confidence interval, and p-value will be presented.

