 - Subjects with 0%, >0% and <20%, ≥20% and <40%, ≥40% and <60%, ≥60% and <80%, ≥80% and <100%, ≥80% and ≤100%, and 100% product use adherence. For the purposes of the frequency table, each compliance group will be deemed mutually exclusive.
- Similar to the FDA primary endpoint analysis, failure components of the primary endpoint (i.e., CT infection, GC infection, use of prohibited antibiotics, lost to follow-up, or invalid CT/GC test at Visit 5) will be summarized using frequencies and percentages with the difference between treatment groups analysed using a Chi-Square test. The Fisher's Exact test will be conducted in place of the Chi-Square test if necessary due to issues with the expected cell counts.
- Responses to the PROMIS SexFS Satisfaction, Pain and Lubrication subscales with EVO100 vaginal gel usage and placebo at each visit will be summarized using count and percentage. Descriptive summary will also be provided using the derived subscale scores (refer [section 7.1](#)). In addition, the shifted change from baseline to post baseline response will also be summarized.
- Response to FSFI questionnaire- Lubrication and Pain subscales with EVO100 vaginal gel usage and placebo at each visit will also be summarised using count and percentage. Response to questions 7, 8, 9, 10 will be considered for lubrication subscale and questions 17, 18 and 19 will be considered for pain subscales from the FSFI questionnaire. In addition, the shifted change from baseline to post baseline response will be summarized.
- Patient Global Impression of Change (PGIC) with EVO100 vaginal gel usage versus placebo will be summarized by treatment group.

Validation related analyses for the patient-reported outcomes (FSFI, product satisfaction questionnaire, PROMIS SexFS etc.) referenced here will be outlined in a separate psychometric analysis plan.

Listings will be provided for PROMIS SexFS, FSFI, product satisfaction questionnaire and PGIC.

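### The FSFI pain and lubrication, PROMIS SexFS and PGIC endpoints are worded as EVO100-versus-placebo comparisons, but SAP 8.6.3 plans only by-arm descriptive summaries, with no pre-specified, baseline-adjusted difference or confidence interval.

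*SAP*

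**What the plan says.** Three exploratory endpoints in SAP 4.3 are worded as contrasts between arms:

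- FSFI: "Comparison of FSFI Lubrication and Pain subscales with EVO100 vaginal gel usage versus placebo".
- PROMIS SexFS: the entry ends "Pain and Lubrication subscales with EVO100 vaginal gel usage versus placebo".
- PGIC: "Comparison of Patient Global Impression of Change (PGIC) with EVO100 vaginal gel usage versus placebo".

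The exploratory outcome list in the protocol synopsis uses equivalent wording for all three.

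SAP 8.6.3 splits the exploratory endpoints into two lists. After the first list it says "Above endpoints will be compared against placebo based on Chi-Square test", with an estimated difference, 95% confidence interval and p-value. That list holds the sexual satisfaction item with and without absence of infection, product satisfaction, and the primary endpoint by prior infection documentation. The three instruments come in the second list:

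- FSFI: "Lubrication and Pain subscales with EVO100 vaginal gel usage and placebo at each visit will also be summarised using count and percentage", plus shifts from baseline.
- PROMIS: counts and percentages, shifts from baseline, and "Descriptive summary will also be provided using the derived subscale scores".
- PGIC: "Patient Global Impression of Change (PGIC) with EVO100 vaginal gel usage versus placebo will be summarized by treatment group".

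The matching displays in SAP section 10 (Tables 14.2.3.2 to 14.2.3.8) are titled only as summaries or shifts. In the assessment schedule (SAP Table 2), FSFI is collected at screening, enrollment and every later visit, and PROMIS at screening, enrollment, Visit 5 and Visit 6.

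**The concern.** The endpoint list and the analysis section do not match. The endpoints are contrasts with placebo, but no effect measure, interval or model is specified for them, and SAP section 9 does not record a change from comparison to description.

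Pain and lubrication during sex are of interest for a gel applied before each act of intercourse, and the data to estimate an arm difference well, including a pre-randomisation score, are already being collected. If the method stays open, the visit, the score and the model can be chosen after unblinding. The report would then show by-arm tables with no agreed statement of how large a difference the data support or rule out.

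**Working it through.** **1. Endpoint wording against planned analysis**

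| Instrument | SAP 4.3 | SAP 8.6.3 | Difference or CI | Baseline used in an arm contrast |
|---|---|---|---|---|
| FSFI pain, lubrication | comparison | counts, shifts | none | no |
| PROMIS SexFS | comparison | counts, score summary, shifts | none | no |
| PGIC | comparison | summary by group | none | not applicable |

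Elsewhere 8.6.3 says so when a between-arm result is intended. The adherence categories get a difference, interval and p-value. The failure components get a Chi-Square test, although 4.3 calls that analysis descriptive.

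**2. Could another section supply the estimate?** SAP 8.1 offers confidence intervals only where relevant and names no effect measure for these endpoints. The separate psychometric plan is for validation analyses. The genitourinary adverse event summaries in 8.7.1 are descriptive. None fills the gap.

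**3. The plan's own sample size.** The documents give no figure for these endpoints. For the primary endpoint, SAP section 5 assumes failure rates of 37.5% and 30.5%, two-sided 5% and about 85% power. With mean rate 0.34:

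n = [1.96·√(2·0.34·0.66) + 1.036·√(0.375·0.625 + 0.305·0.695)]² / 0.07² ≈ 821 per arm, as stated.

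**4. Precision that an added estimate would have.** The number of women with Visit 5 scores is not given. As a rough proxy, take the planned primary successes: 0.695·821 ≈ 570.6 on EVO100 and 0.625·821 ≈ 513.1 on placebo.

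- Standard error in SD units: √(1/570.6 + 1/513.1) = 0.0608.
- Unadjusted half-width: 1.96·0.0608 = 0.119 SD.
- Adjusted for baseline at correlation r: 0.119·√(1 − r²).

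| r | Half-width (SD) | Power for a true 0.1 SD | Power for a true 0.2 SD |
|---|---|---|---|
| 0 (unadjusted) | 0.119 | 37.6% | 90.8% |
| 0.3 | 0.114 | 40.6% | 93.1% |
| 0.5 | 0.103 | 47.5% | 96.7% |
| 0.7 | 0.085 | 63.4% | 99.6% |

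Power is Φ(d/SE − 1.96), with SE = 0.0608·√(1 − r²).

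With equal response in both arms instead, the unadjusted half-width is 1.96·√(2/n): 0.097 SD at 100% of 821, 0.108 SD at 80% (657) and 0.125 SD at 60% (493).

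**5. Are the scores in SAP 7.1 ready for such an analysis?** Not yet.

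- *FSFI lubrication.* The score is 0.3 times the sum of Q7 to Q10. As coded, low values are good for Q7 and Q9 but bad for Q8 and Q10. Best lubrication scores (1+5+1+5)·0.3 = 3.6 and worst scores (5+1+5+1)·0.3 = 3.6. With all four items in the same direction the two would be 6.0 and 1.2.
- *Zero responses.* In both FSFI subscales, 0 means no sexual activity or no attempt at intercourse. A woman with no attempt has a pain score of 0·0.4 = 0, below the (1+1+1)·0.4 = 1.2 of a woman with the worst answer to every item.
- *PROMIS.* The T-scores exist only for women reporting sexual activity. The protocol synopsis and 8.6.3 name a Satisfaction subscale, but 7.1 gives no scoring for it and Table 14.2.3.2 omits it.
- *Observation.* Under the protocol synopsis (Treatment Duration), participation ends at a positive CT or GC test, so who has a Visit 5 score can depend on treatment.

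**The case against.** The strongest reply is that nothing was promised beyond description. SAP 4.3 also calls the compliance endpoint a comparison, and 8.6.3 summarises it descriptively, so a reader who infers that 4.3 commits the sponsor to a test or an estimate goes further than the SAP's own usage. The endpoints are exploratory and outside the testing hierarchy. This part stands: rewording 4.3 would cure the mismatch, though it would leave the data under-used.

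A reader might also infer that the trial could say nothing about how the gel changed pain or lubrication. The documents do not support that. SAP 8.1 requires n, mean and SD by arm for continuous variables, PROMIS scores and PGIC are summarised by arm, and Table 14.2.3.5, listed separately from the all-questions table, points to FSFI subscale summaries. An unadjusted difference and interval can be computed from such figures. Nor are the PROMIS satisfaction items unreported, since Table 14.2.3.3 covers all questions.

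It would likewise be too much to call these the trial's local-tolerability measures. The SAP treats them as patient-reported outcomes, PGIC is a global item, and local symptoms are also summarised as genitourinary adverse events.

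Finally, primary successes are a weak proxy for respondents. Women who fail through prohibited antibiotics or an invalid test may still attend, and early-termination visits follow Visit 5 procedures. The range of response rates shown above answers this without changing the conclusion.

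**Conclusion.** The point holds as a low-severity gap in specification. For all three instruments the SAP names a contrast with placebo and then specifies no between-arm estimate, no interval and no use of the baseline scores in one. The primary conclusion is not affected.

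On the assumed 571 and 513 respondents, an unadjusted interval would extend about 0.12 SD either side, and 0.114 to 0.085 SD after baseline adjustment at correlations of 0.3 to 0.7. A shift near 0.2 SD could be shown or excluded. A reader might infer that 0.1 SD could be too. It could not reliably be: the half-width is above 0.1 SD unless the baseline correlation is high, and power at 0.1 SD is about 38% unadjusted. Respondent numbers and correlations are assumptions; the documents give neither. The figures also presuppose a valid score, which FSFI lubrication as now coded is not.

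**What to change.** First, in SAP 7.1 and section 10:

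- Reconcile the response coding of FSFI Q7 and Q9 with Q8 and Q10.
- Treat zero responses (no activity, no attempt) as not applicable, not as low scores.
- State that the scores are conditional on sexual activity and on remaining under observation.
- Add PROMIS Satisfaction scoring to 7.1 and to Table 14.2.3.2.

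Then, in SAP 8.6.3, report at Visit 5:

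- *FSFI pain and lubrication scores:* the EVO100 minus placebo difference with 95% CI from a repeated-measures model over Visits 2 to 5, with terms for pre-randomisation score, visit, arm, arm by visit and prior infection documentation stratum.
- *PROMIS T-scores:* the same difference from an ANCOVA with the same baseline and stratum adjustment. It uses only women with a Visit 5 score, so the observation caveat matters most here.
- *PGIC:* a proportional-odds or rank-based effect with 95% CI.

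Label all of these nominal and exploratory, and keep the count and shift tables. If the sponsor wants description only, the lesser remedy is to reword 4.3 accordingly and record the change in section 9.

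The cost is SAP text, the scoring decisions above and a few more model outputs from data already collected. The downside is a few more nominal exploratory results.

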5 SAMPLE SIZE AND POWER

The primary analysis is a comparison between proportion of subjects who are defined study successes versus study failures (success defined as subjects completing the trial to Visit 5 without any CT or GC infection and no use of prohibited antibiotics; failures defined as subjects with CT infection, GC infection, use of prohibited antibiotics, or loss to follow-up) among the intervention groups (EVO100 or placebo).

It is assumed that the proportion of subjects who will have CT infection, GC infection, use of prohibited antibiotics, or loss to follow-up will be 30.5% for active treatment versus 37.5% for placebo group based on the Phase 2B/3 study (EVO003) with equal lost to follow-ups assumed in both intervention groups. Using a Chi-Square test for the primary endpoint, 821 analyzable subjects per treatment group (1642 subjects total) will yield approximately 85% power to detect a rate difference of 7% with a 2-sided 5% type I error rate. Given the assumption that 5% of subjects are found to be positive at enrollment, the total sample size planned for this study is 1730 subjects. With an assumed screen failure rate of approximately 27.8%, 2397 subjects are estimated to be needed for screening.

6 ANALYSIS POPULATIONS

This study will utilize three analysis populations: Intention-to-treat (ITT), modified Intention-to-Treat (mITT), and safety.

6.1 Intention-To-Treat Population (ITT)

The ITT population is defined as all randomized subjects. Analyses with this population will be performed based on the treatment randomized.

6.2 Modified Intention-To-Treat Population (mITT)

The mITT population is defined as all randomized subjects who are negative for chlamydia and gonorrhoeae at enrollment and are provided with study product. Analyses with this population will be performed based on the treatment randomized.

6.3 Safety Population (Safety)

Safety population will be based on subjects documented to have been distributed any study product. Subjects with proof that no study product was taken (e.g., all study drug returned) will not be included in the Safety population. Analysis with this population will be performed based on the treatment actually received.

6.4 Protocol Deviations/Violations and Exclusions from Analysis Sets

A cumulative list of protocol deviations will be reported in the Clinical Study Report.

